Alcohol Dependence Scale (ADS) is a 25 item to measure severity of alcohol dependence; the Alcohol Use Questionnaire (AUQ) consists of 8 items to determine the respondent's alcohol craving; Smoking History Questionnaire

Abstinence Measures:

Clinical Institute Withdrawal Assessment-Alcohol Revised (CIWA-Ar) is a 13 item scale that measures alcohol withdrawal signs and symptoms. The assessment will be administered at intake and weekly.

Urine Toxicology and Breathalyzer Screening: A urine toxicology screen will be conducted at intake to confirm alcohol use. During treatment, urines will be collected 3 times weekly to confirm sobriety during inpatient stay using the CNRU laboratory. In addition, urine samples will be taken 2 times weekly during outpatient treatment and at follow-up appointments using on-site TESTCUP5 Drug Screen (Roche Diagnostics Inc., Totowa, NJ) to monitor opiate and other drug use. The TestCup5 kit provides results for opioids, cocaine, THC, PCP and barbiturates. In addition, breath alcohol levels will also be assessed with the Alcosensor III Intoximeter at each face-to-face contact, 2 times weekly.

Assessment of Psychological Symptoms:

A number of self report measures of psychological functioning will be obtained weekly to examine Prazosin's effects on psychological functioning. The following well-established and reliable instruments will be used:

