with medication and alcohol withdrawal/anxiety, we used a conservative effect size of $d = .60$ for detection of significant main effects and possible interactions in the clinical trial. At this effect size and power = .80, with $p < .05$, sample size estimates from Cohen (1988, p.258) indicated that we would require 25 subjects per cell to adequately assess the proposed hypotheses for the clinical trial (total $N = 100$). Including a 15-20% drop-out after enrollment, we estimated recruitment of 120 AD patients into the trial to ensure adequate power for the trial.

Data Analysis for Laboratory Study: Repeated measures ANOVA and mixed model procedures to assess treatment group differences in alcohol craving and stress related changes (heart rate, blood pressure, HPA and catecholamine responses) during laboratory exposure to stress and drug cues as compared to neutral imagery conditions. Non-parametric tests will be used to assess occurrence of side effects, treatment retention rates, alcohol use measures, CIWA scores and perceived stress scores during the outpatient treatment phase. The number and type of AE's for the two treatment groups will be conducted using t-tests, chi-square tests and ANOVAs as appropriate. Findings will be used to estimate effect sizes for the medication and guide the larger randomized clinical trial.

Data Analysis for the 12-week clinical trial Study: For this phase, the following moderator and primary and secondary outcomes are specified:

Primary Moderator Measure: Alcohol withdrawal symptoms, as measured by the CIWA alcohol withdrawal scale,

Primary Outcome Measures in the outpatient treatment phase: These are: (1) Heavy drinking days (5 or more for men, 4 or more for women) during the 12 week period, and (2) Any drinking days. Both will be assessed daily using smartphone or interactive voice recording surveys completed by the patients and also with weekly urine drug screens/breathalyzer reports and self report of drug use on the Substance Use Calendar.

Secondary Outcome Measures in the outpatient treatment phase: Secondary outcome measures will include alcohol craving scales, anxiety (Hamilton Anxiety Scale) and depression (CES-D) and sleep quality using the Pittsburgh Sleep Quality Index – PSQI).

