Data Analytic Procedures: Since patients will be randomly assigned to the Prazosin and PLA treatment groups and Intent-to-Treat (ITT) analyses will be conducted for the clinical outcomes. We do not expect the groups to be different on demographic, prior drug use history or other predictor variables. Nevertheless, prior to undertaking the specific analysis for each aim, we will compare the treatment groups on demographic variables, substance use characteristics and previous psychiatric history/predictor variables using t-tests/chi-square analyses as appropriate. If any group differences are found, the specific variable will be entered as a covariate in all of the specific analyses. As there are no established thresholds for AW effects on drinking outcomes in outpatient treatment, baseline AW will be assessed as continuous measure in all overall analyses. Thus, intent-to-treat (ITT) analyses with baseline AW severity (mean-centered continuous CIWA-Ar scores) as a moderator of Time (Pre-Full Dose(FD): weeks 1-2; Post FD: weeks 3-12) were conducted with linear or generalized linear mixed effect (LME/GLME) piecewise growth models for continuous and binary outcomes. Due to a positive skew, number of drinks per day

(AvgD) will be log-transformed. Control variables in all analyses will be gender (0=male), inpatient (0=outpatient), and dropout (0=completer, 1=dropout/withdrawn prior to 4 weeks, 2=dropout/withdrawn after 4 weeks). For secondary outcomes linear mixed models with random intercepts will be used to assess the effect of AW, Treatment and Week (factor 1-12, or Weeks 4, 8 and 12) on the secondary outcome variables. All control variables from the main outcome analyses are included in the secondary outcome analyses. If significant interactions with AW are observed for primary or secondary outcome analyses, a median split of AW scores will be conducted to obtain Low and High AW groups and assess contrasts by treatment.

Aims and Hypotheses for Laboratory and Treatment Outcome Components: All analyses of the laboratory and the treatment components will be based on the following specific aims and hypotheses:

Specific Aim 1: To evaluate the effects of Prazosin on stress-induced alcohol craving and associated neuroadaptations in alcohol dependent individuals. Hypothesis 1: Prazosin will decrease stress-induced alcohol craving and negative emotions in the laboratory as compared to placebo.

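### Secondary outcomes are modelled with random intercepts and no serial covariance; if weekly scores are serially correlated, the 12-level Treatment x Week tests would run at about 7-13% rather than 5%

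*Combined protocol and SAP*

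**What the plan says.** The relevant text is in the combined protocol and SAP, Section V, item 12 (Statistical Considerations).

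- **Outcomes.** "Secondary outcome measures will include alcohol craving scales, anxiety (Hamilton Anxiety Scale) and depression (CES-D) and sleep quality" (PSQI).
- **Model (Data Analytic Procedures).** "For secondary outcomes linear mixed models with random intercepts will be used to assess the effect of AW, Treatment and Week". Week enters in one of two codings: "Treatment and Week (factor 1-12, or Weeks 4, 8 and 12) on the secondary outcome variables". The text does not say which outcome gets which coding. The control variables from the main analysis are carried over.
- **Frequency (Assessment of Psychological Symptoms).** "A number of self report measures of psychological functioning will be obtained weekly", so the 12-level coding is a real planned case.
- **Follow-up of interactions.** "If significant interactions with AW are observed for primary or secondary outcome analyses", alcohol withdrawal (AW) is split at its median and the treatments are contrasted within the low and high groups.
- **Laboratory part.** "Repeated measures ANOVA and mixed model procedures to assess treatment group differences in alcohol craving and stress related changes". Sphericity is not mentioned.

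Nowhere does the plan give a within-patient correlation, a residual covariance structure, a robust standard error or a degrees-of-freedom method for these models. It does not write out a Treatment x Week term either. That test is implied by putting Treatment and Week in one longitudinal model.

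**The concern.** A random intercept with independent residuals is compound symmetry: weeks 1 and 2 are assumed to be as correlated as weeks 1 and 12. If correlation decays with lag, the 11 Treatment x Week contrasts carry unequal and dependent variation. The F test still counts them as 11 equally informative degrees of freedom, so its critical value is too low.

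At stake are claims that prazosin changes the course of craving, anxiety, depression or sleep over the 12 weeks, and claims that this change depends on withdrawal severity. A false positive in an AW interaction that involves Week could also open the median-split contrasts.

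**Working it through.** The plan states no error rate or correlation for these models, so there is no figure of its own to reproduce.

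**Inputs**

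- From the documents: p = 12 weekly levels, or 3 levels (weeks 4, 8, 12); 100 evaluable patients (25 in each of 4 cells), so 50 per arm; 120 recruited with 15-20% drop-out; 75 per arm in the dosing table; nominal level 0.05 from the power section.
- Assumed: no treatment effect, and AR(1) correlation between weekly scores of 0.3 to 0.9.

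**Step 1: degrees of freedom.** With complete data, the random-intercept test of Treatment x Week is the uncorrected split-plot F test, on p - 1 = 11 and (100 - 2) x 11 = 1078 degrees of freedom. Its 5% critical value is 1.798. Let S be the within-patient covariance after centring over weeks. Box's factor is

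ε = (tr S)² / [(p - 1) tr(S²)],

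and the actual level is approximately P[F(11ε, 1078ε) > 1.798]. At correlation 0.5, ε = 0.673. The test then has about 11 x 0.673 = 7.4 effective numerator degrees of freedom, and the tail probability is 8.0%.

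**Step 2: simulation.**

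| AR(1) | ε | Box level | Treatment x Week, complete data, 50 or 75 per arm | Same test, REML fit, 20% drop-out, 60 per arm | Treatment x AW x Week, 50 per arm |
|---|---|---|---|---|---|
| 0.3 | 0.87 | 6.1% | 6.0-6.2% | 6.2% | not run |
| 0.5 | 0.67 | 8.0% | 7.8-8.1% | 7.4% | 8.0% |
| 0.7 | 0.47 | 11.0% | 10.4% | 11.1% | 9.6% |
| 0.8 | 0.37 | 12.7% | 11.0-11.6% | 13.9% | 11.1% |
| 0.9 | 0.29 | 14.4% | 12.7% | 13.4% | 13.8% |

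Runs per setting were 10,000, 2,000 and 4,000 for the last three columns. At 2,000-4,000 runs the simulation standard error near 13% is 0.5-0.8 points, so the entries just under 14% do not differ clearly from 13%. Where compound symmetry truly holds, the test runs at 4.9-5.1%. Adding a true stable person effect to the AR(1) changes little (7.6-8.0% at 0.5, 12.5-13.4% at 0.9), so the random intercept does not absorb the problem. If the departure is a random slope instead, the level is 4.5-7.3% over the slope variances tried.

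**Step 3: source of the inflation.** Under no effect, the interaction and error mean squares agree (0.847 against 0.849 at 0.5; 0.685 against 0.691 at 0.7). The average error variance is therefore right. What is overstated is the degrees of freedom.

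**Step 4: intervals.** In units of the outcome variance, the model takes 1 - r̄ as half the variance of any week-to-week difference, where r̄ is the mean off-diagonal correlation. The true value is 1 - ρ^lag. At ρ = 0.5, r̄ = [2/(12 x 11)] Σ (12 - k) 0.5^k = 0.152, so 1 - r̄ = 0.848.

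- Weeks 1 and 12: true value 1 - 0.5^11 = 0.9995. The standard error is √(0.848/0.9995) = 0.92 of what it should be, and a nominal 95% interval covers about 93%. At ρ = 0.7 it covers about 90%.
- Adjacent weeks: true value 0.5. The standard error is √(0.848/0.5) = 1.30 times too large, and coverage is about 99%.
- Treatment difference at week 12 alone: simulated coverage 94.8-95.2%.

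**Step 5: tests that are not affected.** With complete data the Treatment main effect compares patient averages, so the lag structure does not bias it. Simulation gives 4.6-5.3% (4.9-5.3% with drop-out, AR(1) 0.3-0.9). The omnibus test at weeks 4, 8 and 12 gives 4.5-5.7% (Box at most 5.9%). Within that coding, the single contrast of week 12 with week 4 reached 7-9% at weekly correlation 0.7-0.9.

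**Step 6: after correction.** At AR(1) 0.5 / 0.7 / 0.9 with 12 weeks and 50 per arm, an unstructured covariance gives 5.2 / 4.8 / 5.2%, and a Greenhouse-Geisser correction gives 5.3 / 4.5 / 4.9%. The random intercept plus AR(1) fit was not simulated; it matches the structure assumed here.

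**The case against.** The strongest reply is that the size depends on a correlation the documents do not supply, and that the affected test is not one the plan writes out. Both points are true. The plan lists effects of AW, Treatment and Week, and only AW interactions trigger follow-up. Treatment and Treatment x AW compare patients with one another and are not exposed to this fault. The weeks 4, 8 and 12 coding barely shows it.

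What remains is that the plan commits to random intercepts and offers a 12-level Week factor. Any test of whether the treatment difference changes over those weeks therefore inherits the problem.

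Three stronger readings may tempt a reader, and the documents support none of them:

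- *Secondary p-values are too small in general.* The main effect and the three-occasion omnibus test are sound.
- *All secondary intervals are too narrow.* Those between distant weeks are, those between adjacent weeks are too wide, and the single-week difference is right.
- *The laboratory tests will be run uncorrected.* The text names repeated measures ANOVA alongside mixed models and does not mention sphericity, so this is an omission rather than a stated uncorrected test. Peak and area-under-the-curve summaries are also planned for the hormone and catecholamine measures. These remove the within-session time factor.

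**Conclusion.** The point holds in conditional form and for secondary outcomes only. For outcomes coded with 12 weekly levels, the named model gives omnibus Treatment x Week and Treatment x AW x Week tests a level of about 7-13% instead of 5%, if serial correlation is 0.5-0.9 and decays roughly as AR(1). At 0.3 the level is about 6%, and under true equal correlation it is 5%. The plan gives no reason to expect equal correlation over 12 weeks. The fault is worth correcting because a usable alternative exists and the present wording fixes the weaker choice.

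**What to change.** In Data Analytic Procedures, replace the random-intercept wording with:

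- **Weekly outcomes:** random intercept plus AR(1) residual, or an unstructured covariance. The unstructured form has 12 x 13 / 2 = 78 covariance parameters, so name AR(1) as the fallback if it fails to converge.
- **Outcomes at weeks 4, 8 and 12:** unstructured covariance.
- **Both:** Kenward-Roger degrees of freedom.

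State which outcome uses which coding of Week, and write out the interaction terms to be tested. In Data Analysis for Laboratory Study, state that any repeated measures ANOVA over the session time points will carry a Greenhouse-Geisser correction.

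This needs no new data and no more patients. The cost is SAP wording and some less favourable secondary p-values. Setting the structure before analysis also prevents it from being chosen after the results are seen.

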This aim will be tested using mixed model analysis of variance procedures for each of the following dependent measures: VAS alcohol craving scale; VAS anxiety scale; brief CCQ; DES emotions of anger, sadness and fear; heart rate, blood pressure and HPA measures of ACTH and cortisol and NE and EPI.

Specific Aim 2: To evaluate the efficacy of Prazosin versus Placebo in high alcohol withdrawal individuals on primary outcomes of: (a) heavy drinking days (HDD) over 12 week period; (b) Any drinking days (DD%).

Hypothesis 2: In high alcohol withdrawal individuals, Prazosin group will show significant reductions in HDD% and DD% during the 12 week treatment period as compared to Placebo group. No differences between medication treatment groups in the Low alcohol withdrawal individuals will be observed.

Secondary outcome measures such as alcohol craving, Anxiety, depression and sleep quality will be assessed. Findings PSS, COPE and LES scores will be examined.

SECTION VI: RESEARCH INVOLVING DRUGS, BIOLOGICS, RADIOTRACERS, PLACEBOS AND DEVICES
--

If this section (or one of its parts, A or B) is not applicable, state N/A and delete the rest of the section.

A. DRUGS, BIOLOGICS and RADIOTRACERS

1. **Identification of Drug, Biologic or Radiotracer:** What is (are) the **name(s)** of the drug(s) biologic(s) or radiotracer(s) being used? Identify whether FDA approval has been granted and for what indication(s).

Prazosin (marketed by Pfizer Inc) is an alpha-1-adrenergic agonist that is known to preferentially bind to post-synaptic alpha1-adrenergic receptors. Walker et al (2008) found that Prozaosin was effective in suppressing excessive alcohol consumption in rats, suggesting the involvement of the noradrenergic system in alcohol dependence. Simpson et al. (2007) found similar findings in a pilot trial using prozosin for treatment of alcohol dependent men and women. Prazosin therefore is an excellent candidate for treating alcohol seeking behaviors. It may also be more easily tolerated than those medications which directly modulate these transmissions.

All protocols which utilize a drug, biologic or radiotracer **not** approved by, but regulated by, the FDA, or a radiotracer regulated by the RDRC, must provide the following information:

- What is the Investigational New Drug (IND) **number** assigned by the FDA? N/A
- Who holds the IND?
- All protocols which utilize a radiotracer not approved by, but regulated by the FDA must provide the IND number: _____

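### No single Treatment x AW contrast is named as the test of Hypothesis 2, and nothing says whether one or both primary outcomes must succeed, so a claim of moderation by withdrawal is not held at 5%

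*Combined protocol and SAP*

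**What the plan says.** All of this is in Section V, item 12 (Statistical Considerations).

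- **Primary outcomes.** They are listed as "These are: (1) Heavy drinking days (5 or more for men, 4 or more for women) during the 12 week period, and (2"; the second item is any drinking days. No order or success rule follows.
- **Model.** Data Analytic Procedures fits piecewise growth models with two time pieces, weeks 1-2 (before full dose) and weeks 3-12 (after it). Mean-centred continuous CIWA-Ar is the moderator. A log-transformed number of drinks per day is also mentioned, although it is not a declared primary outcome.
- **Trigger for the treatment contrasts.** "If significant interactions with AW are observed for primary or secondary outcome analyses, a median split of AW scores will be conducted". The noun is plural, no term is named, and secondary outcomes count as well as primary ones.
- **Hypothesis 2.** In high-AW patients prazosin is to reduce HDD% and DD% compared with placebo; in low-AW patients no difference is expected.
- **Significance level.** It appears only in the power text: "At this effect size and power = .80, with $p < .05$, sample size estimates from Cohen (1988, p.258) indicated" the required number. Sidedness is not given, and the analysis text states no level.
- **Other tests.** The laboratory paragraph adds "Non-parametric tests will be used to assess occurrence of side effects, treatment retention rates, alcohol use measures" and further items in the outpatient phase. For Aim 1, "This aim will be tested using mixed model analysis of variance procedures for each of the following dependent measures", with no primary measure named.

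**The concern.** Hypothesis 2 is the trial's efficacy claim, and it depends on moderation by AW. A piecewise model offers several places for that moderation to appear: the starting level, the early slope and the late slope, in each of two outcomes. The trigger is not even restricted to interactions that involve treatment.

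With no term and no outcome fixed in advance, the choice could be made after the data are seen. The .05 in the power text is the level of one test, whereas the rule as written lets any of several tests lead to a claim. A report that withdrawal severity moderates the response to prazosin could then rest on whichever outcome or time piece crossed .05.

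**Working it through.** **1. The plan's own figure.** The plan gives no overall error rate. Its only calculation at .05 is the sample size for d = .60 with power .80. For one two-sided comparison of two arms:

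n per arm = 2(1.960 + 0.842)² / 0.60² = 2 x 7.85 / 0.36 = 43.6, so 44 per arm, 88 in total, or 22 per cell of a 2 x 2.

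The plan has 25 per cell and a total of 100, which is somewhat more. The relevant point is that .05 enters as the level of a single test.

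**2. Inputs for the error rate.**
- From the plan: two primary outcomes, two time pieces, and 120 recruited (power text).
- Assumed: two-sided .05; one, two or three Treatment x AW terms per outcome; correlation ρ between the outcomes' test statistics. HDD are a subset of DD, so independence is implausible, and .5 to .9 is a reasonable range.

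**3. One term per outcome.** P(at least one significant) = 1 - P(|z1| < 1.96 and |z2| < 1.96), with bivariate normal z. P(both significant) = .05 + .05 - P(at least one).

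| ρ | At least one | Both |
|---|---|---|
| 0 | 1 - .95² = 9.75% | 0.25% |
| .5 | 9.1% | 0.9% |
| .7 | 8.3% | 1.7% |
| .8 | 7.8% | 2.2% |
| .9 | 7.0% | 3.0% |

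An either-outcome rule therefore gives about 7% to 9% over the assumed range, and just under 10% at independence. A both-outcomes rule on one named term stays below 5%.

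**4. Several terms per outcome.** This is a null simulation with 120 patients allocated 1:1, a break at week 2, and no treatment or AW effect. Treatment x AW is tested on each term, and a trial counts if any term in either outcome is significant.

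- Three terms (start, early slope, late slope): about 13% in one outcome alone. In either of two outcomes: 22.9% (ρ = .5), 20.9% (.7), 18.5% (.85). Repeat runs differ by a point or so; dropping the week-0 observation gives about 17% to 20%.
- Two terms (the two slopes): about 13% to 17% for ρ from .85 to .5.

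The independence ceilings are 1 - .95⁴ = 18.5% for four tests and 1 - .95⁶ = 26.5% for six; the simulated rates lie below them, as they should. Secondary outcomes, which the trigger also admits, are not counted.

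**5. Both outcomes required, but any term allowed in each.** The same simulation with three terms gives about 4% to 7%. A both-required rule alone does not guarantee 5% while the term is unnamed.

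**6. The full Hypothesis 2 pattern.** Count a null trial only if the interaction is significant in the favourable direction and prazosin is also significantly better in the High-AW half. With N = 120, one interaction and one High-AW contrast per outcome, this happens on either outcome in 0.9% to 1.1% of trials (ρ = .8 to .5), and on both in about 0.1%. If each of six terms had one such contrast, the union bound is about 3.5%.

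**7. Aim 1.** The list has 12 measures: VAS craving, VAS anxiety, brief CCQ, three emotions, heart rate, blood pressure, ACTH, cortisol, NE and EPI. If all were independent, 1 - .95¹² = 46%. That is only a ceiling, since several are closely related.

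**The case against.** A reader might infer that the trial's false-positive rate is 8% to 23% instead of 5%. The documents do not support that, for four reasons.

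- The number of terms, the correlation and the test level are all assumptions. The starting-level interaction in particular is not mentioned in the text; AW is described as moderating two time pieces.
- Hypothesis 2 joins HDD% and DD% with the word and. If both are required on one named term, the rate is about 1% to 3% over the assumed correlations.
- The median split is a follow-up. The complete Hypothesis 2 result needs the interaction and then a favourable High-AW contrast, which is rare under the null (step 6).
- The stated purpose is preliminary efficacy, so strict control may seem more than is needed.

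The first and third points stand: the higher rates belong to a bare claim of moderation, not to Hypothesis 2 as a whole. The second stands only in part, because the wording is a prediction and not a decision rule, and step 5 shows that it does not settle the matter while the term is open. The fourth affects how strict to be. It is no reason to leave the test unnamed, and the monitoring section calls this a phase II efficacy study.

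A reader might also infer that the primary outcomes have two competing analyses. The non-parametric sentence is in the laboratory paragraph, whose stated use is effect-size estimation and planning of a larger trial, and it names neither HDD nor DD. It is an ambiguity, and none of the rates above includes it. For Aim 1, Hypothesis 1 already narrows the claim to stress-induced craving and negative emotions, and the laboratory sample size uses the craving effect size (f = .44).

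**Conclusion.** The gap is real: two primary outcomes, an open set of AW interactions, and no named test, order or success rule. If any one significant interaction is taken as evidence of moderation, the false-positive rate for that statement is about 7% to 10% with one term per outcome and about 14% to 23% with two or three. This assumes two-sided .05 and between-outcome correlations of roughly .5 to .9, with the 10% end reached only near independence. The plan fixes none of these inputs, so the figures show how much depends on the missing rule; they do not measure the plan's actual error rate. The full Hypothesis 2 pattern has a null rate of about 1% with one High-AW contrast per outcome, and more contrasts would raise it. The non-parametric and Aim 1 points are minor.

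**What to change.** Change the SAP wording in Data Analytic Procedures and Specific Aim 2:

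1. Name one Treatment x AW contrast, tied to a stated time piece or period average, as the test of Hypothesis 2, at two-sided .05.
2. Test HDD% first, and DD% with the same contrast only if HDD% succeeds. Alternatively, state that both must succeed on that contrast.
3. Let only that contrast support the confirmatory High/Low AW comparison. Label every other interaction, including those in secondary outcomes and in drinks per day, exploratory.
4. Minor: label the non-parametric tests of outpatient alcohol use as supportive. For Aim 1, name stress-induced alcohol craving as the primary measure and specify the scale, since Aim 1 lists a VAS whereas Laboratory Assessments describes the AUQ.

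No extra patients are needed to hold the level. The cost of the fixed sequence is that DD% cannot be claimed alone if HDD% fails; the cost of requiring both is lower power. Splitting alpha at .025 each would keep both outcomes open, but even a simple two-arm comparison at d = .60 would then need 2(2.241 + 0.842)² / 0.36 = 52.8, so 53 per arm instead of 44.

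### Hypothesis 2 is judged on withdrawal groups cut at the sample median; effects from the continuous model at CIWA-Ar values fixed in advance would answer it better

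*Combined protocol and SAP*

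**What the plan says.** All of this is in Section V, item 12 (Statistical Considerations).

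- **Reason for a continuous score.** Data Analytic Procedures states: "As there are no established thresholds for AW effects on drinking outcomes in outpatient treatment, baseline AW will be assessed as continuous measure". The mixed models take "baseline AW severity (mean-centered continuous CIWA-Ar scores) as a moderator of Time".
- **Follow-up.** The same paragraph adds a second step, for primary and secondary outcomes alike, which is triggered only when the AW interaction reaches significance: "a median split of AW scores will be conducted to obtain Low and High AW groups and assess contrasts by treatment".
- **Hypothesis.** Specific Aim 2 is "To evaluate the efficacy of Prazosin versus Placebo in high alcohol withdrawal individuals" on the two primary drinking outcomes. Hypothesis 2 predicts benefit in the high-withdrawal patients and adds: "No differences between medication treatment groups in the Low alcohol withdrawal individuals will be observed".

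No CIWA-Ar value defines High or Low, no rule covers scores equal to the median, and no treatment effect at stated CIWA-Ar values is planned. The only CIWA bands in the documents (8 to 12, and 13 or above, in Section V, item 9, Alcohol Detoxification) serve withdrawal management.

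**The concern.** The argument for leaving AW uncut in the main model applies equally to the step that follows it. If no cut point is established for drinking outcomes, the sample median is not one either. Yet the median split produces the contrasts that decide Hypothesis 2, so here it does more than display a result.

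Three consequences follow. A high-withdrawal patient is one above whatever median this sample has, so a clinician elsewhere cannot tell whether a new patient belongs to the group. Patients just either side of the median are treated as different, while those far apart on the same side are treated as alike. With whole-number scores, many patients may sit exactly at the median, and the plan does not say which group takes them. Meanwhile the model already fitted can supply a treatment effect at any withdrawal score, often with better precision.

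**Working it through.** **Inputs.** From the Power Analysis: d = .60, power .80, p < .05 (I take it as two-sided), 25 per cell, N = 100, and 120 recruited to allow for dropout. The enrolment target elsewhere is 150 (Section VII, item 1; 75 per arm in the dosing table). The baseline CIWA-Ar distribution is not given, so every figure that depends on its shape is an assumption.

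**The plan's own figure.** Two-sided at d = .60, a comparison of two arms needs 45 per arm by the t test (90 in total). A 2 x 2 F test with f = d/2 = .30 needs 23 per cell (92 in total). The stated 100 is not reproduced exactly and is slightly generous, with power about .84. The 120 is consistent with dropout of 16.7% (100/0.833).

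**Information kept by a median split.** For a linear moderator, the share kept when the High-Low difference is read from two halves is the squared correlation between the score and its High/Low indicator.

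| Assumed shape | Kept | Lost |
|---|---|---|
| Uniform | .75 | 25% |
| Normal (2/π) | .637 | 36% |
| Gamma, shape 2 | .553 | 45% |
| Exponential ((ln 2)²) | .480 | 52% |
| Gamma, shape 0.5 | .368 | 63% |
| Lognormal, σ = 1 | .274 | 73% |

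**Ties.** For illustrative whole-number scores (negative binomial, mean 3, shape 1), assigning tied scores to Low or to High makes the High group 42% or 56% of patients and the loss 45% or 57%.

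**Like-for-like precision of the High-group answer.** Assume a normal score, a linear AW effect, one outcome per patient, unit residual SD, equal arms and a fitted treatment-by-AW term.

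- Split contrast, 25 v 25: variance 1/25 + 1/25 = .080, SE .283. Power = Φ(.60/.283 − 1.96) = Φ(.16) ≈ .56 (.55 by the t test).
- Model-based effect at z SDs above the mean score: variance (4/N)(1 + z²). The High group's mean is at z = √(2/π) ≈ .80, so the variance is .04 × 1.64 = .0656, SE .256. Power = Φ(.60/.256 − 1.96) = Φ(.38) ≈ .65.
- Ratio .0656/.080 = .82, or 18% less variance.
- At z = 1 the variance is .04 × 2 = .080, equal to the split. At z = 2 it is .04 × 5 = .20 (SE .447), clearly worse.
- At N = 150 before dropout, the split gives 4/75 = .0533 and power about .74. The model at z = .80 gives (4/150) × 1.64 = .0437 and Φ(.60/.209 − 1.96) ≈ .82.

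**The case against.** The strongest reply is that the split is a conditional follow-up used to describe an interaction already found on the continuous scale, which is common practice. That is right for the main test: "baseline AW will be assessed as continuous measure in all overall analyses", so the test of moderation is untouched.

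Three stronger readings should be resisted.

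- A reader might infer that the plan's moderator test drops from .80 power to .61 (normal score) or .49 (exponential), by Φ(2.80 × √kept − 1.96). Those would be the powers of an interaction tested on a dichotomised score. The plan contains no such test, and the documents give no CIWA-Ar distribution to support either figure.
- A reader might blame the split for the power of about .55 in the High group. Most of that shortfall comes from having 25 v 25. The continuous model recovers only part of it.
- A reader might say the paragraph contradicts itself by denying that any threshold exists. It says only that none is established for drinking outcomes in outpatient treatment. This is an inconsistency of reasoning, not a flat contradiction.

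The alternative also has limits. An effect at one withdrawal score is a different quantity from a group-mean contrast, and it depends on the linear AW term. Sample percentiles move with the sample just as the median does. The values 8 and 13 come from withdrawal management, and baseline data near 13 may be sparse. These limits affect how the remedy is specified; they do not rescue the split as the definition of Hypothesis 2's groups.

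**Conclusion.** The point holds as a weakness of the follow-up analysis, not of the interaction test. Hypothesis 2 is answered on groups that are set by the sample, lack a tie rule and cannot be applied elsewhere, although the plan's own reasoning argues against a cut.

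The gain in precision from the alternative is real but modest: about 18% less variance at the High group's mean score, or power of about .65 v .56 at N = 100. This assumes a normal score, d = .60 and a linear AW effect; it ignores repeated measures and dropout. There is no gain at +1 SD and a loss beyond it. The information lost by splitting is about 36% if scores are normal and 52% if exponential, with 25% to 73% across the other shapes tried. None of these is a known figure for this trial. The main benefit is interpretability: a result tied to stated CIWA-Ar scores can be used by others. I rate it a cheap improvement worth making.

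**What to change.** - Keep the continuous interaction test as planned.
- Answer Hypothesis 2 with treatment effects and 95% confidence intervals from that model, at one lower and one higher CIWA-Ar value fixed in advance and inside the well-populated range. A Johnson-Neyman region can be added.
- Prefer stated CIWA-Ar values to sample percentiles. Use 8 and 13 only as reference points, and only if the baseline data cover them.
- Check linearity of the AW term, for example with a spline or quadratic term, and say what will be reported if it fails.
- If the median split is kept, label it descriptive and state which group takes scores equal to the median.

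The cost is a few sentences in the SAP and a little extra analysis, with no change to data collection or sample size. The downside is reliance on the linear AW term.
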